7.4 Statistical Analyses for Efficacy

Summary and Analysis of the Primary Endpoint

Analysis of the primary endpoint will be conducted based on mITT population. No formal statistical testing will be performed, and descriptive statistics will be tabulated. Observed data will be used without imputation.

Summary and Analysis of Secondary and Additional Endpoints

Analysis of the secondary and additional endpoints will be conducted based on mITT population. Descriptive statistics will be tabulated and observed data will be used without imputation.

Additional details will be provided in the SAP.

7.5 Statistical Analyses for Safety

The safety analyses will be performed using the safety population. For each safety endpoint evaluating change from baseline, the last non-missing safety assessment before study drug administration will be used as the baseline for all analyses of that endpoint.

Treatment-emergent AEs (TEAEs) are defined as any AE with the onset that is after the first dose of study drug. Events in which the onset date is the same as the study drug start date are assumed to be treatment-emergent, unless known to have started prior to study drug administration.

An overview of AEs will be presented consisting of the number and percentage of subjects experiencing at least one event for each of the following AE categories:

- Any TEAE
- Any TEAE related to study treatment according to the investigator
 - Any TEAE related to study drug according to the investigator
 - Any TEAE related to study procedure according to the investigator
- Any mild TEAE
 - Any mild TEAE related to study treatment according to the investigator
- Any moderate TEAE
 - Any moderate TEAE related to study treatment according to the investigator
- Any severe TEAE
 - Any severe TEAE related to study treatment according to the investigator
- Any serious TEAE
 - Any serious TEAE related to study treatment according to the investigator
- Any TEAE leading to death
- Any PDSOT TEAE
- All deaths

Treatment-emergent adverse events will be summarized by system organ class (SOC) and PT; for TEAEs related with reasonable possibility to study treatment (including study drug related and study procedure related) as assessed by the investigator by SOC and PT; for maximum severity by SOC and PT; and for subject numbers by SOC and PT. Specific TEAEs will be counted once for each subject for calculating percentages, unless stated otherwise. In addition, if the same AE occurs multiple times within a subject, the highest severity and level of relationship to study treatment will be reported.

Treatment-emergent SAEs (including deaths) will be summarized by SOC and PT. All SAEs will be provided in listing format.

Possible distant spread of toxin TEAEs will be identified in the SAP and summarized by PT.

7.6 Interim Analysis

Not applicable for this study.

7.7 Overall Type I Error Control

Not applicable for this study.

7.8 Sample Size Determination

No formal sample size calculation was performed.

For a conservative expected proportion of 75% for the primary endpoint (proportion of subjects reporting *Mostly satisfied* or *Very satisfied* on the FLSQ Follow-up Item 4 at Day 30), a sample size of 100 subjects in the study is required for an adjusted logit-based 95% binomial confidence interval to have a width of 16.8% (interval is 75% – 9.1% to 75% + 7.7% with recommended correction of – 1/2).⁹

8 ETHICS

8.1 Independent Ethics Committee/Institutional Review Board (IEC/IRB)

The protocol, informed consent form(s), recruitment materials, and all subject materials will be submitted to the IEC/IRB for review and approval. Approval of both the protocol and the informed consent form(s) must be obtained before any subject is enrolled. Any amendment to the protocol will require review and approval by the IEC/IRB before the changes are implemented to the study. In addition, all changes to the consent form(s) will be IEC/IRB approved.

8.2 Ethical Conduct of the Study

The study will be conducted in accordance with the protocol, Operations Manual, International Council for Harmonisation (ICH) guidelines, applicable regulations, and guidelines governing clinical study conduct and the ethical principles that have their origin in the Declaration of Helsinki. The responsibilities of the investigator are specified in [Appendix B](#).

In the event a significant disaster/crisis (e.g., epidemic/pandemic, natural disaster, conflict/combat) occurs leading to difficulties in performing protocol-specified procedures, AbbVie may engage with study site personnel in efforts to ensure the safety of subjects, maintain protocol compliance, and minimize risks to the integrity of the study while trying to best manage subject continuity of care. This may include alternative methods for assessments (e.g., phone contacts or virtual site visits), and alternative locations for data collection (e.g., use of a local lab instead of a central lab). In all cases, these alternative measures must be allowed by local regulations and permitted by IRB/IEC. Investigators should notify AbbVie if any urgent safety measures are taken to protect the subjects against any immediate hazard.

8.3 Subject Confidentiality

To protect subjects' confidentiality, all subjects and their associated samples will be assigned numerical study identifiers or "codes." No identifiable information will be provided to AbbVie.

9 SOURCE DOCUMENTS AND CASE REPORT FORM COMPLETION

The investigator is responsible for ensuring the accuracy, completeness, legibility, and timeliness of the data reported. All source documents should be attributable, legible, contemporaneous, original, accurate, and complete to ensure accurate interpretation of data. Clinical site monitoring is conducted to ensure that the rights and well-being of human subjects are protected, that the reported trial data are accurate, complete, and verifiable, and that the conduct of the trial is in compliance with the currently approved protocol, ICH Good Clinical Practice (GCP), and applicable local regulatory requirement(s). During the COVID-19 pandemic, remote data review/verification may be employed if allowed by the local regulatory authority, IRB/IEC, and the study site.

10 DATA QUALITY ASSURANCE

AbbVie will ensure that the clinical trial is conducted with a quality management system that will define quality tolerance limits in order to ensure human subject protection and reliability of study results. Data will be generated, documented, and reported in compliance with the protocol, ICH GCP, and applicable regulatory requirements.

11 COMPLETION OF THE STUDY

The end-of-study is defined as the date of last visit of the last subject in the study.

APPENDIX A. STUDY-SPECIFIC ABBREVIATIONS AND TERMS

| Abbreviation | Definition |
|--------------|--|
| AE | adverse event |
| AGLSS | Allergan Glabellar Line Severity Scale |
| COVID-19 | coronavirus disease 2019 |
| DHEA | dehydroepiandrosterone |
| eCRF | electronic case report form |
| EDC | electronic data capture |
| FDA | Food and Drug Administration |
| FHL | forehead lines |
| FHLSS | Forehead Line Severity Scale |
| FLSQ | Facial Line Satisfaction Questionnaire |
| FSH | follicle-stimulating hormone |
| GCP | Good Clinical Practice |
| GL | glabellar lines |
| ICH | International Council for Harmonisation |
| IEC | independent ethics committee |
| IMP | investigational medicinal product |
| IRB | institutional review board |
| IUD | intrauterine device |
| LCL | lateral canthal lines |
| LCLSS | Lateral Canthal Line Severity Scale |
| MedDRA | Medical Dictionary for Regulatory Activities |
| mitT | modified intention-to-treat |
| N/A | not applicable |
| NTEA | Neurotoxin Treatment Experience Assessment |
| PCR | polymerase chain reaction |
| PDSOT | possible distant spread of toxin |
| PRO | patient-reported outcome |
| PT | preferred term |
| RSI | reference safety information |
| SAE | serious adverse event |
| SAP | statistical analysis plan |

| | |
|------------|---|
| SAR | serious adverse reaction |
| SARS-CoV-2 | severe acute respiratory syndrome coronavirus 2 |
| SOC | system organ class |
| SUSAR | suspected unexpected serious adverse reaction |
| TEAEs | treatment-emergent adverse events |
| U | units |
| UFL | upper facial lines |
| VDS | verbal descriptor scale |
| WOCBP | women of childbearing potential |

APPENDIX B. RESPONSIBILITIES OF THE INVESTIGATOR

Protocol M22-974: A Prospective, Multi-center, Open-label Study to Evaluate Subject Satisfaction and Natural Outcomes Following Administration of BOTOX® Cosmetic (Botulinum Toxin Type A) Purified Neurotoxin Complex in Subjects with Upper Facial Lines (Glabellar Lines, Lateral Canthal Lines, and Forehead Lines)

Protocol Date: 14 December 2023

Clinical research studies sponsored by AbbVie are subject to the International Council for Harmonisation of Technical Requirements for Pharmaceuticals for Human Use (ICH) Good Clinical Practices (GCP) and local laws and regulations and guidelines governing the study at the site location. In signing the Investigator Agreement, the investigator is agreeing to the following:

1. Conducting the study in accordance with ICH GCP, the applicable regulatory requirements, current protocol and operations manual, and making changes to a protocol only after notifying AbbVie and the appropriate Institutional Review Board (IRB)/Independent Ethics Committee (IEC), except when necessary to protect the subject from immediate harm.
2. Personally conducting or supervising the described investigation(s).
3. Informing all subjects, or persons used as controls, that the drugs are being used for investigational purposes and complying with the requirements relating to informed consent and ethics committees (e.g., IEC or IRB) review and approval of the protocol and its amendments.
4. Reporting complaints that occur in the course of the investigation(s) to AbbVie.
5. Reading the information in the Investigator's Brochure/safety material provided, including the instructions for use and the potential risks and side effects of the investigational product(s).
6. Informing all associates, colleagues, and employees assisting in the conduct of the study about their obligations in meeting the above commitments.
7. Maintaining adequate and accurate records of the conduct of the study, making those records available for inspection by representatives of AbbVie and/or the appropriate regulatory agency, and retaining all study-related documents until notification from AbbVie.
8. Maintaining records demonstrating that an ethics committee reviewed and approved the initial clinical protocol and all of its amendments.
9. Reporting promptly to AbbVie, the ethics committee/institutional review boards (as required) and other appropriate individuals (e.g., coordinating investigator, institution director):

APPENDIX D. ACTIVITY SCHEDULE

The following tables show the required activities across the study. The individual activities are described in detail in the **Operations Manual** ([Appendix E](#)). Allowed modifications due to COVID-19 are detailed in the Operations Manual.

APPENDIX E. PROTOCOL SUMMARY OF CHANGES

Previous Protocol Versions

| Protocol | Date |
|-------------|--------------|
| Version 1.0 | 03 June 2022 |
| Version 2.0 | 26 June 2023 |

The purpose of this version is to correct minor clerical errors for consistency throughout the protocol in addition to the following:

1. Protocol (Title Page) and Operations Manual ([Appendix F](#), Section 1 and Section 4.2) were updated to reflect the current Sponsor/emergency medical and non-emergency contacts.
2. Protocol (Section [3.4](#)) and Operations Manual ([Appendix F](#), Section 3.6) were updated to correct measurement of efficacy onset from "Day 1 up to Day 14" to "Day 2 to Day 15."
3. Protocol (Section [4.1](#)) was updated to allow more flexibility in enrollment and to reflect review of site data.
4. Protocol (Section [5.1](#), eligibility criterion #3) was updated for consistency with the Operations Manual ([Appendix F](#), Section 3.1). Eligibility criterion #8 was updated for clarity.
5. Protocol (Section [5.2](#)) was updated to provide additional language for females on hormone replacement therapy whose menopausal status is in doubt.
6. Protocol (Section [5.7](#)) and Operations Manual ([Appendix F](#), Section 6.2, Section 6.3, and Section 6.6) were updated, as the study drug will be sourced commercially.
7. Protocol (Section [6.1](#)) was updated to clarify that partner pregnancy information will not be collected.
8. Operations Manual ([Appendix F](#), Section 3.11) was updated to remove a sentence regarding images captured on Day 1. A sentence was added to allow for image collection to be repeated within 7 days as needed.

1.0 Introduction

This Statistical Analysis Plan (SAP) describes the statistical analyses for Study M22-974: A Prospective, Multi-center, Open-label Study to Evaluate Subject Satisfaction and Natural Outcomes Following Administration of BOTOX® Cosmetic (Botulinum Toxin Type A) Purified Neurotoxin Complex in Subjects with Upper Facial Lines (Glabellar Lines, Lateral Canthal Lines, and Forehead Lines).

Study M22-974 examines subject satisfaction and natural outcomes following simultaneous treatment of multiple upper facial lines (GL, LCL, and FHL) with 64 U of BOTOX Cosmetic.

The SAP will not be updated in case of administrative changes or amendments to the protocol unless the changes impact the analysis.

Unless noted otherwise, all analyses will be performed using SAS Version 9.4 (SAS Institute Inc., Cary, NC 27513) or later.

2.0 Study Design and Objectives

2.1 Objectives and Hypotheses

The primary objective of this study is to evaluate subject satisfaction and natural outcomes following simultaneous treatment of multiple upper facial lines (GL, LCL, and FHL) with 64 U of BOTOX Cosmetic by Facial Line Satisfaction Questionnaire (FLSQ) Item 4 at Day 30 based on the modified Intent-to-Treat (mITT) population, which consists of all enrolled subjects who receive the total dose of 64U of BOTOX cosmetic.

2.2 Study Design Overview

This is a 6-month, prospective, multicenter, open-label study to evaluate subject satisfaction and natural outcomes following the administration of BOTOX Cosmetic 64 U for the treatment of upper facial lines.

The study will enroll approximately 100 subjects with moderate to severe GL, LCL, and FHL as assessed by the investigator. Out of the approximately 100 enrolled subjects:

- approximately 20% of the study population will be treatment naïve to any botulinum toxin of any serotype for any indication,
- approximately 20% of the study population will be self-identified as male,
- approximately 20% of the study population will be self-identified as Asian, and
- approximately 20% of the study population will have Fitzpatrick skin phototypes of IV, V, or VI.

On Day 1, after subjects are verified to meet all eligibility criteria and have completed all baseline study procedures, they will receive 64 U of BOTOX Cosmetic. Each subject will receive a total of 16 injections (0.1 mL or 4 U of BOTOX Cosmetic per injection), with 5 injections in the glabellar complex, 3 injections in the lateral canthal area on each side (6 total injections), and 5 injections in the frontalis muscle.

There are seven in-clinic visits: screening/baseline/treatment (Day 1), post-treatment follow-up visits (Days 30, 60, 90, 120, 150), and study exit (Day 180 or Early Exit). The study schema of the study is shown in [Figure 1](#).

Figure 1. Study Schema

2.3 Treatment Assignment and Blinding

This is an open-label study. Hence, there is no subject randomization or blinding for the study treatment assignment.

2.4 Sample Size Determination

No formal sample size calculation was performed.

For a conservative expected proportion of 75% for the primary endpoint (proportion of subjects reporting *Mostly satisfied* or *Very satisfied* on the FLSQ Follow-up Item 4 at Day 30), a sample size of 100 subjects in the study is required for an adjusted logit-based 95% binomial confidence interval to have a width of 16.8% (interval is 75% - 9.1% to 75% + 7.7% with recommended correction of - 1/2).¹

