8.0 Handling of Potential Intercurrent Events for the Primary and Key Secondary Endpoints

Observed data will be used without imputation, so subjects who have an intercurrent event resulting in not having FLSQ Item 4 at Day 30 for any reason will not be included in the primary efficacy endpoint. Intercurrent events include:

- Subjects who are enrolled but do not receive any study drug;
- Subjects who are enrolled and treated but prematurely discontinue the study before assessment of the primary endpoint;
- Subjects who die before assessment of primary endpoint;
- Subjects who are lost to follow-up and are missing assessment of primary endpoint;
- Subjects who are missing assessment of primary endpoint for any other reason (including COVID) not mentioned above
 - The same approach will be used for the secondary analysis.

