9.0 Efficacy Analyses

9.1 General Considerations

The following considerations apply to all efficacy analyses, unless otherwise specified:

- All efficacy analyses will be conducted in the mITT population unless otherwise specified.
- Day 1 is defined as the day on which the study treatment is first received.

- Baseline for effectiveness parameters will be the last non-missing assessment prior to or on Day 1.
- Study day is always relative to Day 1.
- Change from baseline will be computed as postbaseline minus baseline.
- Continuous variables will be summarized descriptively using number of subjects with observed values (n), mean, standard deviation (SD), median, minimum (min), and maximum (max). In addition, 95% confidence intervals (CIs) will be performed using paired t-tests for change from baseline endpoints.
- Categorical variables will be summarized descriptively using number of subjects with observed values or events (n) and the percentage of subjects with observed values or events.
- Analyses based on responder rates will include a 95% CI for the responder rate using the exact binomial distribution (Clopper-Pearson approach).
- All CIs will be 2-sided 95% CIs, unless stated otherwise.

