9.2 Handling of Missing Data

No imputation of missing data will be made for the efficacy analyses.

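### The 16.8% confidence-interval width behind N = 100 belongs to a different interval from the Clopper-Pearson one the SAP will report, which is about 1 point wider at the planning rate of 75%

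*SAP*

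**What the plan says.** **Precision statement.** SAP 2.4, repeated in Protocol 7.8, says no formal sample size calculation was done. It then gives a precision argument. The rate is an assumption ("For a conservative expected proportion of 75% for the primary endpoint"), and 100 subjects are described as "required for an adjusted logit-based 95% binomial confidence interval to have a width of 16.8" percent. The limits around that rate are also spelled out: "interval is 75% - 9.1% to 75% + 7.7% with recommended correction of - 1/2".

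**Interval to be reported.** SAP 9.1 sets a general rule: "Analyses based on responder rates will include a 95% CI for the responder rate using the exact binomial distribution (Clopper-Pearson approach"). The primary endpoint (SAP 3.1 and 9.3.1) is a responder status, so the rule covers it. SAP 9.1 and 13.0 make all intervals two-sided 95% unless stated otherwise.

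**Denominator.** SAP 2.2 counts enrolled subjects: "The study will enroll approximately 100 subjects with moderate to severe GL, LCL, and FHL as assessed by the investigator". SAP 4.0 limits the mITT population to those who receive the full 64 U. For the primary endpoint, SAP 8.0 then says "subjects who have an intercurrent event resulting in not having FLSQ Item 4 at Day 30 for any reason will not be included". On the same point, SAP 9.2 adds "No imputation of missing data will be made for the efficacy analyses". Neither document gives an expected rate of missing Day 30 data, or says that the 100 in the precision statement means evaluable subjects.

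**The concern.** In a single-arm study with no hypothesis test, the expected interval width is the only quantitative support for the sample size. Here that width is calculated for one interval and the analysis section specifies another. Clopper-Pearson guarantees at least nominal coverage and pays for this in width, so the direction of the mismatch is predictable: the reported interval will be wider than the plan says for the same data. The sample-size sentence also treats all 100 enrolled subjects as evaluable, whereas the analysis uses observed cases only.

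At stake is whether the plan agrees with itself. A reader who applies SAP 9.1 to the plan's own scenario of 75 responders in 100 will not get 16.8%, and nothing in either document explains why. The responder estimate itself is unaffected.

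**Working it through.** **Inputs.** Planning rate 75%, N = 100, correction −1/2 and stated limits −9.1/+7.7 (SAP 2.4, Protocol 7.8); two-sided 95%, z = 1.96; Clopper-Pearson for analysis (SAP 9.1). Evaluable numbers below 100 are assumptions.

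**1. Reproduce the stated figure.** Adjusted logit with x = 75, n = 100 and the correction applied to the centre:

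- Centre: ln[(75 − 0.5)/(25 − 0.5)] = ln(74.5/24.5) = 1.1121
- Standard error: √(1/75 + 1/25) = 0.2309
- Logit limits: 1.1121 ± 1.96 × 0.2309 = 0.6595 and 1.5648
- Back-transformed: 65.91% to 82.70%, which is −9.1/+7.7 around 75%, width 16.79%

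This matches the plan, so the 16.8% is right for its own method.

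**2. The interval SAP 9.1 will report.** The Clopper-Pearson limits are beta quantiles: lower = B(0.025; x, n − x + 1), upper = B(0.975; x + 1, n − x). At 75/100 they are 65.34% and 83.12%, that is −9.7/+8.1, width 17.78%. The excess over the reproduced figure is 17.78 − 16.79 = 0.99 points.

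**3. Same counts, both methods (100 evaluable).**

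| Responders | Adjusted logit width | Clopper-Pearson width | Gap |
|---|---|---|---|
| 75/100 | 16.79 | 17.78 | 0.99 |
| 80/100 | 15.53 | 16.52 | 0.99 |
| 85/100 | 13.89 | 14.89 | 1.00 |

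**4. When does Clopper-Pearson meet 16.8% with 100 evaluable?** At 79/100 the interval is 69.71% to 86.51%, width 16.80%. It meets the figure from 79 responders upward. Taking the responder count as Binomial(100, p), the chance of a width above 16.8% is the chance of 78 or fewer responders:

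| True rate | Expected Clopper-Pearson width | P(width > 16.8%) |
|---|---|---|
| 75% | 17.67 | 0.789 |
| 80% | 16.40 | 0.346 |
| 85% | 14.75 | 0.039 |

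**5. Fewer evaluable subjects (loss rates assumed).**

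| Assumed loss | Count at 75% | Clopper-Pearson width | First count at about 16.8% |
|---|---|---|---|
| 4% | 72/96 | 18.16 | 77/96 = 80.2% (width 16.81) |
| 8% | 69/92 | 18.56 (64.89 to 83.45) | 75/92 = 81.5% (width 16.78) |
| 12% | 66/88 | 18.99 | 73/88 = 83.0% (width 16.68) |

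The 77/96 entry is 16.81, so it meets 16.8 only to one decimal; the strict count is 78/96 (width 16.50).

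**6. Number implied by the stated width.** A Clopper-Pearson width of 16.8% at 75% needs about 112 evaluable subjects (84/112 gives 16.77). This only sizes the mismatch; it is not a proposal to enrol more.

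**The case against.** The strongest reply is that nothing here is miscalculated and nothing depends on it. The plan names its method and gets the right answer for it. It disclaims a formal sample size calculation, calls 75% conservative, and plans no test, interim analysis or type I error control. At rates somewhat above 75%, Clopper-Pearson with 100 evaluable subjects is inside 16.8% anyway. All of that stands, and it makes this a mismatch between planning and analysis rather than an arithmetic slip.

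The attrition figures are assumed. Day 30 is the first scheduled visit after a single treatment, enrolment is only approximate, and Protocol 4.1 lets sites enrol more subjects with sponsor approval, so the evaluable number need not fall below 100. That also stands. The 1-point gap at 75/100 does not depend on attrition.

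On the remedy, Protocol 8.1 requires ethics review of any protocol amendment, which is heavy for an illustrative width. The SAP version history also shows that the Clopper-Pearson sentence arrived in version 2.0 (17 March 2025), after the protocol date of 14 December 2023, so overwriting Section 2.4 could obscure how N was first supported. Both are fair points about how to make the correction. They do not remove the inconsistency: the current SAP states one width and plans an interval that does not deliver it at the stated rate.

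**Conclusion.** The concern holds. At the planning rate of 75% with all 100 subjects evaluable, the planned Clopper-Pearson interval is 17.8% wide against the stated 16.8%, a gap of about 1 point that is due to the method alone. Observed-case losses would add to it: 18.2% to 19.0% for assumed losses of 4% to 12%. The shortfall against 16.8% is specific to rates near 75%; with 100 evaluable it disappears from 79 responders upward.

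The practical effect is small. No decision, test or estimate changes. The correction is still worth making because this is the only precision figure supporting N, and a reader cannot reproduce it from the analysis the SAP specifies.

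**What to change.** In SAP 2.4, give the expected precision for the interval that will be reported, with its assumptions. For example:

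> With 100 evaluable subjects and an observed responder rate of 75%, the exact (Clopper-Pearson) two-sided 95% CI is 65.3% to 83.1% (width 17.8%). With 92 evaluable subjects (69/92) it is 64.9% to 83.4% (width 18.6%). At 80/100 it is 70.8% to 87.3% (width 16.5%).

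The adjusted-logit figure can stay beside it, labelled as the basis used at planning, so that the record of how N was supported is kept. Protocol 7.8 can take the same text at its next amendment; an amendment for this alone is not needed.

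The alternative is to name the adjusted-logit interval for the primary endpoint in SAP 9.1 and state that 16.8% assumes 100 evaluable subjects and an observed rate of 75%. That changes the reported interval, so the first option is the lighter one.

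Cost of the first option: a short statement in each document. Enrolment, data collection and analysis are unchanged.
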